9.4.3 ANALYSIS OF THE SECONDARY ENDPOINT(S)

For secondary endpoints, a similar GEE-based approach will be used. Within- and between- group comparisons will be analyzed based on coefficients in the model. This approach also allows for flexibility with missing data. Unstandardized beta coefficients will be presented with 95% confidence intervals and p-values (<0.05 will be considered statistically significant).

For non-repeated continuous measures (e.g., delirium duration, cumulative opioid consumption) and binary outcomes (e.g., postoperative delirium, headache), we will use the same GEE modeling approach. All GEE models will use the empirical parameter estimates with an exchangeable correlation matrix. As indicated previously, models will adjust for baseline cohort imbalances. Additionally, for Quality of Recovery and headache severity, the differential effect of habitual caffeine consumption and group will be tested. This will be tested via interaction term of habitual caffeine consumption with caffeine group (placebo, low-dose caffeine group, high-dose). The daily number of caffeinated beverages will be recorded for each participant, and the resulting distribution will be analyzed and used to inform the most appropriate categorization of habitual caffeine users (e.g., non-users, low-dose, high-dose, etc.).

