1 PROTOCOL SUMMARY

1.1 SYNOPSIS

Title:	The CAffeine, Postoperative delirium, And CHange IN Outcomes after Surgery-2 (CAPACHINOS-2) Study
Study Description:	The objective of this study is to test the effects of caffeine on neurocognitive and clinical recovery after major surgery. Specifically, this trial tests the primary hypothesis that caffeine will reduce the incidence of postoperative delirium.
Objectives:	
Primary objective: The primary objective is to determine whether postoperative caffeine reduces the incidence of postoperative delirium, based on standardized delirium assessment methodology.
 
Secondary Objectives: To determine (1) whether caffeine improves postoperative patient satisfaction, based on validated, patient-reported quality of recovery measures, and (2) neural correlates of delirium and Mild Cognitive Impairment, based on advanced electroencephalographic (EEG) analysis.

Endpoints:	
Primary Endpoint: Incidence (%) of postoperative delirium, measured via long-form Confusion Assessment Method (CAM).¹
 
Secondary Endpoints:
 
-- Delirium severity (CAM-S)²-- Delirium duration (days, n)-- Patient-reported 15-item Quality of Recovery score³-- Agitation (via Richmond Agitation and Sedation Scale, RASS)⁴-- Sedation (via Richmond Agitation and Sedation Scale, RASS)⁴-- Headache severity (10-centimeter visual analog scale, VAS)-- Cumulative opioid consumption (oral morphine equivalents, mg)

The CAffeine, Postoperative Delirium, And CHange IN Outcomes after Surgery-2 (CAPACHINOS-2) Study Protocol <2.0>

[figure not shown]
Version <2.0>
<14 December 2022>

Study Population:	In total, surgical patients (n=250; ≥70 years of age) presenting for major non-cardiac, non-intracranial neurologic surgery will be recruited at Michigan Medicine.
Phase:	2
Description of Sites/Facilities Enrolling Participants:	Study operations will be conducted at Michigan Medicine University Hospital and Cardiovascular Center; Ann Arbor, MI USA.
Description of Study Intervention:	This will be a three-arm parallel trial. Participants will be randomized to intravenous dextrose 5% in water (placebo), low-dose caffeine citrate (1.5 mg/kg), or high-dose caffeine citrate (3 mg/kg) at multiple postoperative time points over a 30-minute infusion period.
Study Duration:	The estimated trial duration will be approximately four years.
Participant Duration:	Total study duration for patients will be approximately 30 days.

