4.2 SCIENTIFIC RATIONALE FOR STUDY DESIGN

This trial will follow conventional (rather than adaptive) methodologies, for the following reason: even if caffeine is not found to reduce risk of postoperative delirium, secondary outcomes (e.g., quality of recovery, headache) may nonetheless suggest benefit and warrant further analysis. Lastly, multiple dosing arms will help to elicit optimal dosing strategies for maximizing the benefit-to-risk ratio across outcomes.

The control group will not receive either caffeine intervention and will remain at standard risk for perioperative complications previously outlined. However, control group patients will nonetheless receive standard perioperative care that would otherwise be received without trial enrollment. Dextrose 5% in water (D5W) was chosen as the placebo intervention, as caffeine citrate is soluble in D5W solution.

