8 STUDY ASSESSMENTS AND PROCEDURES

8.1 EFFICACY ASSESSMENTS

The specific timing of procedures/evaluations to be done at each study visit are outlined in **Section 1.3, Schedule of Activities (SoA)**. Details regarding major trial assessment measures are described in the following section.

Screening/Enrollment Visit

Screening visits will be performed during either preoperative clinic visits or on the morning of surgery. Trained research team members will make a determination of study eligibility based on medical chart review and concurrent discussion with potential participants. Screening forms will then be reviewed, confirmed, and signed by the study PI ([name]) anytime between the initial screening visit and surgical intervention. During this initial visit, baseline vitals will be taken and a physical exam will be performed by clinic and perioperative clinicians per clinical standards. Baseline research case report forms will be completed, as outlined in **Section 1.3, Schedule of Activities (SoA)**, by trained research team members.

Delirium Assessments

Delirium will be assessed using the long-form CAM, via in-person assessment, during hospitalization. The CAM strategy will be used to assess delirium severity,² and total delirium duration (days) will also be calculated.

Quality of Recovery

The patient-reported 15-item Quality of Recovery scale will be used.³ This scale has been chosen as a key secondary outcome assessment, as caffeine is postulated to reduce delirium and, potentially, headache, which may help with the recovery process. The scale will be administered preoperatively at baseline and on the second postoperative afternoon. Results will be ascertained and recorded via in-person assessment by the research team.

Agitation and Sedation

Given that caffeine enhances arousal, as described previously, caffeine may also prevent states of obtundation, particularly in the early postoperative setting given the possibility of residual anesthesia.

The Caffeine, Postoperative Delirium, And CHange IN Outcomes after Surgery-2 (CAPACHINOS-2) Study Protocol <2.0>

Version <2.0>
<14 December 2022>

The RASS⁴ will thus be used to assess for agitation (+2 to +4) or sedation (-2 to -5) each timepoint of delirium assessment except for preoperative baseline (where the RASS will not be administered).

Headache

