9.2 SAMPLE SIZE DETERMINATION

Both caffeine groups will be compared to the placebo group based on Generalized Estimating Equation (GEE) modeling. Sample size calculations were thus conducted via GEE Tests for Multiple Proportions in a Cluster-Randomized Design with Power Analysis and Sample Size Software (2022; NCSS, LLC. Kaysville, Utah, USA).⁹⁰ Significance level (α) was set at 0.05. A baseline early postoperative delirium incidence (including the PACU timeframe) of 30% was conservatively estimated based on our preliminary trial.²⁰ A sample size of 250 participants will provide between 80-95% power assuming a baseline delirium incidence of 30%, an incidence ranging between 10-30% in the low-dose group, and an incidence between 10-15% in the high-dose group. These effect sizes are estimated from our preliminary trial data with a similar dosing range (1.7 – 4.5 mg/kg; median dose 2.5 mg/kg) and absolute risk reduction >20%.²⁰ Increased potency may be expected with older patients given the reduced pharmacologic volume of distribution⁷⁴ and a possible age-caffeine interaction effect with respect to cognition.⁷³ This sample size also accounts for an approximate 10% dropout rate. Lastly, no interim analyses are planned in relation to the primary outcome.

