9.4 STATISTICAL ANALYSES

9.4.1 GENERAL APPROACH

For descriptive statistics, categorical outcomes will be presented as proportions (frequencies) and continuous data will be presented as means (\pm standard deviation) or medians (interquartile range). Normality of distribution will be assessed using the Shapiro-Wilk test, and parametric or non-parametric tests will be applied as appropriate. For statistical modeling, covariates will be specified in the following

The Caffeine, Postoperative Delirium, And CHange IN Outcomes after Surgery-2 (CAPACHINOS-2) Study Protocol <2.0>

Version <2.0>
<14 December 2022>

sections. All inferential testing will be two-sided, and p-values <0.05 will be considered statistically significant. 95% confidence intervals will be reported.

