9.4.7 SUB-GROUP ANALYSES

A trial subgroup analysis will be conducted in patients meeting criteria for Mild Cognitive Impairment at preoperative baseline (anticipated n=50)⁹¹ based on preoperative AD8 screening, Montreal Cognitive Assessment score <26, and preserved functional independence via cognitive Independent Activities in Daily Living. This subgroup analysis will test the hypothesis that preoperative Mild Cognitive Impairment will be associated with deviations in baseline neural criticality, based on surrogate electroencephalographic (EEG) measures.^{21,92} As a secondary analysis, we will determine whether caffeine exerts a differential effect on cognitive outcomes in patients with Mild Cognitive Impairment, based on our evidence that caffeine may improve neural criticality, and criticality breakdowns are postulated to underlie Mild Cognitive Impairment and Alzheimer's disease.^{21,92,93} Delirium incidence, severity, and Montreal Cognitive Assessment scores one month post-discharge will also be compared in those with and without baseline Mild Cognitive Impairment.

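### Sections 9.4.1 and 9.4.3 call every secondary test significant at an unadjusted p<0.05, so 14 dose comparisons carry roughly a 26% to 49% chance of at least one false positive if caffeine does nothing

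*Protocol*

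**What the plan says.** The synopsis (1.1) and the objectives table (section 3) list seven secondary endpoints: delirium severity (CAM-S), delirium duration, the 15-item Quality of Recovery score (QoR-15), agitation, sedation, headache severity, and "Cumulative opioid consumption (oral morphine equivalents, mg"). The objectives table puts a separate tertiary/exploratory tier below these seven.

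Section 9.2 says: "Both caffeine groups will be compared to the placebo group based on Generalized Estimating Equation (GEE) modeling". Section 9.4.3 carries this over: "For secondary endpoints, a similar GEE-based approach will be used". Each endpoint therefore yields a low-dose and a high-dose coefficient against placebo.

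The threshold appears twice. The general rule in 9.4.1 is "All inferential testing will be two-sided, and p-values <0.05 will be considered statistically significant". For secondary coefficients, 9.4.3 says "Unstandardized beta coefficients will be presented with 95% confidence intervals and p-values (<0.05 will be considered statistically significant").

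Three other places bear on the point:

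- Section 9.4.3 adds interactions between habitual caffeine use and treatment group for QoR-15 and headache severity. Section 9.4.7 adds a secondary analysis in which "we will determine whether caffeine exerts a differential effect on cognitive outcomes in patients with Mild Cognitive Impairment".
- Section 8.1 says of QoR-15: "This scale has been chosen as a key secondary outcome assessment". No testing order or share of alpha follows from that.
- Section 4.2 justifies a conventional design on the ground that, if delirium is not reduced, "secondary outcomes (e.g., quality of recovery, headache) may nonetheless suggest benefit and warrant further analysis".

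**The concern.** A single per-test threshold over a family of 14 or more tests does not hold the chance of a false finding near 5%. The protocol goes further than leaving multiplicity open, because it states that any secondary coefficient with p<0.05 counts as statistically significant.

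The damaging case is one that 4.2 foresees: delirium is not reduced, but some other recovery measure crosses the threshold. Under the written rule the report may call that a statistically significant effect of caffeine. Nothing in 9.4 tells the reader how many other tests were made or that the p-value is unadjusted.

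**Working it through.** **Inputs from the protocol**

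- Secondary endpoints: 7 (1.1 and section 3).
- Dose comparisons per endpoint: 2 (9.2, carried over by 9.4.3). Tests: 7 × 2 = 14.
- Threshold: two-sided 0.05 per test (9.4.1, 9.4.3).
- Allocation 1:1:1 (4.1). The two dose contrasts share the placebo arm, so their correlation is 0.5.

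**Assumption not in the protocol:** a common correlation ρ between any two endpoints within an arm, varied from 0 to 0.9. CAM-S and delirium duration come from the same CAM assessments, and the RASS is timed with them, so ρ = 0 is the least plausible value for those four endpoints.

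The protocol states no family-wise or secondary error rate, so there is no figure of its own to reproduce.

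**Simple bounds**

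- Expected false positives if caffeine has no effect: 14 × 0.05 = 0.70 per trial, whatever the correlation.
- If all 14 tests were independent: 1 − (1 − 0.05)^14 = 1 − 0.488 = 51.2%.
- One endpoint with two doses sharing placebo: 9.1%.

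**Allowing for correlation.** For dose d and endpoint j, take z = (X_dj − X_0j)/√2, where X is a standard normal arm mean with correlation ρ across endpoints. Over 400,000 simulated null trials, count those with any |z| > 1.96, and separately those with any z > 1.96 in the direction of benefit. For the conditional columns, add the primary as an eighth endpoint with the same ρ and keep only trials in which neither primary dose contrast is significant.

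| ρ | Any of 14 | Any false benefit | Any, given non-significant primary | False benefit, given non-significant primary |
|---|---|---|---|---|
| 0 | 48.6% | 27.7% | 49% | 28% |
| 0.5 | 38.1% | 19.4% | 35% | 18% |
| 0.8 | 25.6% | 12.9% | 20% | 10% |

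At ρ = 0.9 the unconditional figures are 19.9% and 10.1%.

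**Narrower and wider families**

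- Only the two outcomes that 4.2 names (QoR-15 and headache, two doses each, 4 tests): 16% at ρ = 0.5, ranging from 17% at 0 to 14% at 0.8.
- Adding four interaction coefficients (two endpoints by two doses, taken as independent of the main comparisons): 57.5% at ρ = 0, 48.1% at 0.5, 36.0% at 0.8. Four is an inference. The protocol could mean one joint test per endpoint, and 9.4.3 leaves the categories of habitual use to be chosen from the data.
- The number of Mild Cognitive Impairment tests is not fixed, so it is left out.

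For scale, a Bonferroni threshold over 14 tests would be 0.05/14 = 0.0036.

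**The case against.** **Multiplicity rules for secondary endpoints often sit in the analysis plan, which is not at hand.** This is fair as far as silence goes. Here, however, the protocol fixes a rule. A plan that introduced a hierarchy would have to override two protocol sentences, so those sentences need changing in either case.

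**The threshold is an ordinary per-test convention, and no family-wise 5% is promised.** This stands. A reader might describe the error as several times the stated 5%, but the protocol states only a per-test 5%. The point is about how results may be labelled, and no promised level is broken.

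**Section 4.2 is cautious.** This largely stands. A reader might infer that the protocol intends to claim a benefit from secondary endpoints after a negative primary. The text says only that they may suggest benefit and deserve further analysis, which is already partly hypothesis-generating. It is not an exploratory label, though, and 9.4.1 and 9.4.3 do not carry the caution through.

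**The larger percentages do not describe the harm.** Also partly right. The 26% to 49% range counts errors in either direction over the 14 dose tests only. For a false benefit the relevant range is 13% to 28%, or 10% to 28% once the primary is non-significant. Under the correlation model no 14-test figure reaches 50%, so it would be wrong to say that a chance finding is more likely than not. Opioid consumption is also partly a harm question, since the objectives table cites data suggesting an increase.

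**Phase 2 with one declared primary endpoint.** This limits the consequence to secondary claims but does not remove it.

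**Conclusion.** The point holds as a defect in a stated rule. Under 9.4.1 and 9.4.3, with no true effect of caffeine, the 14 dose comparisons give a 38.1% chance of at least one false significant result at ρ = 0.5, ranging from 48.6% at ρ = 0 to 25.6% at ρ = 0.8. For false benefit the figures are 19.4% (27.7% to 12.9%). Given a non-significant primary they are about 18% (28% to 10%).

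These figures rest on an assumed common endpoint correlation, approximately normal test statistics and no effect on any endpoint. If caffeine truly changes some endpoints, fewer null tests remain and the rate falls. Interactions raise it, by an amount that the protocol does not pin down.

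A reader might infer that the protocol sets out to claim a secondary benefit, or that the percentages above already include the interaction and subgroup tests. Neither reading is supported. The change is worth making because it settles what the trial may conclude from these endpoints. Error control on the primary endpoint's two dose comparisons is a separate question.

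**What to change.** 1. In 9.4.1, limit the p<0.05 significance statement to the primary analysis.
2. In 9.4.3, delete the significance threshold. Report secondary endpoints and habitual-caffeine interactions as estimates with 95% confidence intervals. Describe any p-values as nominal, unadjusted for multiplicity and hypothesis-generating.
3. Apply the same wording to the Mild Cognitive Impairment contrasts in 9.4.7.
4. Optional: if a formal secondary claim is wanted, name QoR-15, already singled out in 8.1, as the single secondary endpoint with multiplicity control across the two doses. Whether to gate it on the primary is the sponsor's choice. Gating would rule out a formal QoR-15 claim in the negative-primary case that 4.2 has in mind.

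This is a change of wording, with no added participants or data. The downside is that fewer secondary results can be called statistically significant, including any that point to harm. Those would still be reported with their estimates and intervals.

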To determine whether caffeine impacts sedation or agitation postoperatively	-- Sedation (-2 to -5), Richmond Agitation and Sedation Scale (RASS). Assessed one-hour after PACU arrival and twice daily. Timing will be aligned with CAM delirium assessment. -- Agitation (+2 to +4), RASS. Assessed one-hour after PACU arrival and twice daily. Timing will be aligned with CAM delirium assessment.	As described in the main text, caffeine enhances arousal via key neurochemical pathways. As such, caffeine may mitigate sedation and states related to hypoactive delirium in the early postoperative setting.
To determine whether caffeine reduces risk of perioperative headache	-- Headache severity (n, 10-centimeter VAS) one-hour after PACU arrival and twice daily. Timing will be aligned with CAM delirium assessment.	Preliminary clinical trial data suggest that caffeine can reduce perioperative rebound headache in habitual caffeine users. ²⁵
To determine the effects of caffeine on postoperative opioid consumption.	-- Cumulative opioid consumption, oral morphine equivalents (mg) from PACU arrival through postoperative day two afternoon.	Preliminary data suggest that intravenous caffeine, administered during

The Caffeine, Postoperative Delirium, And CHange IN Outcomes after Surgery-2 (CAPACHINOS-2) Study Protocol <2.0>

Version <2.0>
<14 December 2022>

OBJECTIVES	ENDPOINTS	JUSTIFICATION FOR ENDPOINTS
		early postoperative recovery, may lead to increased postoperative opioid consumption. ²⁰
Tertiary/Exploratory		
To determine the impact of intravenous caffeine on anesthetic emergence profiles	-- Anesthetic emergence time (minutes; time from surgical closure finish to extubation) -- Time from PACU arrival until PACU discharge criteria met (minutes)	Will help to characterize early postoperative arousal and clinical trajectory
To determine whether caffeine reduces the risk of immediate postoperative pulmonary complications	-- Composite outcome: any occurrence of the following airway/pulmonary complications from extubation through PACU stay: airway adjunct use, unplanned continuous positive airway pressure device, unplanned humidified high-flow oxygen, need for bag-mask ventilation, or reintubation.	Given the arousal effects of caffeine previously discussed, caffeine may plausibly mitigate risk of adverse airway and pulmonary complications in the immediate postoperative setting.

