Headache presence and severity will also be assessed (10-centimeter visual analog scale, VAS) at each delirium assessment timepoint. The rationale for this outcome is that perioperative caffeine administration has been demonstrated to reduce rebound headache, particularly in habitual caffeine users.^{25,54}

Opioid Consumption

Perioperative opioid consumption will be collected via electronic medical records and converted to oral morphine equivalents as we have previously described.⁶

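### The listed headache endpoint is repeated VAS severity, but Section 9.4.3 also treats headache as a binary outcome that is never defined

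*Protocol*

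**What the plan says.** The two places in the protocol that list endpoints agree. The synopsis (Section 1.1) has "Headache severity (10-centimeter visual analog scale, VAS" among the secondary endpoints, and the endpoint column of Section 3 has "Headache severity (n, 10-centimeter VAS) one-hour after PACU arrival and twice daily", timed with the CAM. Neither lists headache as present or absent.

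Three other statements do not fit this cleanly:

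- The objective in the same row of the Section 3 table is "To determine whether caffeine reduces risk of perioperative headache".
- Section 8.1 collects two things: "Headache presence and severity will also be assessed (10-centimeter visual analog scale, VAS) at each delirium assessment timepoint".
- Section 9.4.3 names headache as an example of a binary outcome: "binary outcomes (e.g., postoperative delirium, headache), we will use the same GEE modeling approach". Later in the same paragraph it turns to severity: "Additionally, for Quality of Recovery and headache severity, the differential effect of habitual caffeine consumption and group will be tested".

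The common model is given by "All GEE models will use the empirical parameter estimates with an exchangeable correlation matrix", and the common threshold by Section 9.4.1: "All inferential testing will be two-sided, and p-values <0.05 will be considered statistically significant".

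**The concern.** A single named secondary endpoint appears in two forms. The severity form is listed and has a scale and a timetable. The binary form appears only in the analysis section and as the implied meaning of the objective. It does not say what VAS value counts as a headache, over which assessments, or whether the outcome is any headache during follow-up or headache at each visit.

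Both forms could be run under the same GEE approach and judged at p<0.05. If they differ, the protocol text gives some cover for presenting either as the headache result. Section 4.2 makes this worth tidying: it names headache among the secondary outcomes that might suggest benefit and merit further analysis even if delirium is not reduced. The issue is how one secondary result is interpreted. It does not touch the primary endpoint.

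**Working it through.** The protocol gives no headache rate, SD, power or sample size for this trial, so there is no figure to reproduce. The check compares the text, then asks whether the two versions can differ.

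**Step 1: the statements side by side**

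| Place | Form of headache | Defined? |
|---|---|---|
| 1.1, secondary endpoints | VAS severity | Scale given |
| 3, endpoint column | VAS severity, repeated | Scale and timing given |
| 3, objective column | Risk | No |
| 8.1 | Presence and severity collected | No rule for presence |
| 9.4.3, opening sentence | Secondary endpoints in general, by GEE | Covers repeated severity |
| 9.4.3, second paragraph | Binary outcome | No cutoff, window or ever/per-visit rule |
| 9.4.3, same paragraph | Severity, for the interaction | Yes, by reference to the listed endpoint |

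The analysis section is therefore not binary only. It contains both forms and does not say how they relate.

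**Step 2: can the two versions differ on the same patients?** If a visit without headache scores 0, then

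mean VAS = (proportion of visits with headache) × (mean VAS when headache is present).

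The binary analysis sees only the first factor; the severity analysis sees the product. Three patterns with assumed values, none taken from the protocol:

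- A, same frequency, milder headaches on caffeine: placebo 0.30 × 4 = 1.20 cm; caffeine 0.30 × 2.5 = 0.75 cm. Severity differs, presence does not.
- B, fewer but stronger headaches on caffeine: placebo 0.30 × 3 = 0.90 cm; caffeine 0.18 × 5 = 0.90 cm. Presence differs, severity does not.
- C, more but much milder headaches on caffeine: placebo 0.20 × 6 = 1.20 cm; caffeine 0.35 × 2 = 0.70 cm. The two point in opposite directions.

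**Step 3: does this survive the planned type of model?** Placebo was simulated against one caffeine arm.

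- From the protocol: 250 × 0.90 / 3 = 75 per arm (Sections 9.2 and 4.1); 1 + 2 × 3 = 7 postoperative assessments (Section 3); exchangeable GEE with empirical standard errors (Section 9.4.3).
- Assumed: the rates and means above, SD 1.2 cm, latent within-patient correlation 0.4, headache present if VAS >0.
- 150 datasets per pattern, each fitted as continuous VAS and as binary headache, without covariates.

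| Pattern | Severity significant | Binary significant | Decisions differ |
|---|---|---|---|
| No effect (30%, 4 cm in both arms) | 8% | 7% | 3% |
| A | 86% | 3% | 85% |
| B | 4% | 85% | 86% |
| C | 81% | 92% | 27% |

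In C, both were significant in opposite directions in 73% of datasets. With no effect, at least one version was significant in 9%, against 7 to 8% for each alone (Monte Carlo error about 2 points).

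The rows show that disagreement is possible and that the ranking of power reverses between A and B. They are not estimates for this trial.

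**The case against.** The strongest reply is that the protocol already says which version is the endpoint. Both endpoint lists name severity and nothing else. The opening sentence of 9.4.3 covers repeated severity, and the interaction test is on severity. The parenthesis that names headache also names postoperative delirium, which is the primary endpoint, so it reads as a list of variable types and not of secondary endpoints. Section 8.1 plans to record presence, so a binary analysis of it is unsurprising, and its cutoff and window could sit in an SAP that is not shown here.

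Most of this stands. A reader might infer that the protocol never designates a headache endpoint; the two lists rule that out. A missing cutoff would not by itself be a finding either. What remains is that the protocol's own objective and analysis section describe headache in a form its endpoint lists do not contain, and nothing marks that form as supportive. An SAP that chose between them would still leave a protocol sentence contradicted.

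A reader might also infer that the versions are likely to give opposite conclusions, or that one is known to be more powerful. The documents support neither. Significant results in opposite directions appeared only under the special pattern C. The headache rates cited in Section 2.2 (10% vs 23%) come from ambulatory patients at risk of withdrawal headache. This trial enrols patients aged 70 or over with planned admission of at least 72 hours (Section 5.1), habitual caffeine users or not (Section 5.3), and the protocol does not adopt those rates for its own population. A power comparison built on them would also need an assumed severity distribution, and if the effect is placed wholly on presence it favours the presence test by construction.

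**Conclusion.** The inconsistency is real and minor. Severity on the VAS is the listed secondary endpoint. Section 9.4.3 and the Section 3 objective also admit an undefined binary version that could be tested at p<0.05, and the two can disagree on the same data.

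No magnitude is attached. The frequency of disagreement and the ordering of power depend on headache frequency, severity when present and within-patient correlation, none of which the protocol supplies. Under the assumed no-effect case, the chance of at least one significant result was scarcely above that of a single test, so the problem is selective interpretation more than a large rise in false positives. That last remark rests on the assumed values and 150 simulated datasets.

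**What to change.** In Section 9.4.3, take headache out of the binary examples. State that the headache secondary endpoint is VAS severity over the postoperative assessments, analysed by GEE and adjusted for the preoperative headache VAS. That baseline value is already scheduled: Section 1.3 marks a headache assessment at screening, and Section 8.1 ties the VAS to each delirium timepoint. The adjustment is not needed to remove the inconsistency, but it should improve precision and requires no new data.

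Keep headache presence as supportive only, with a fixed definition (for example VAS >0) and a stated time window, reported with a confidence interval. In Section 3, change the objective from risk to severity.

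The cost is a few lines of wording. The one loss is that presence is no longer a formal secondary test.
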